8.2.1.3.2 RELATIONSHIP TO STUDY TREATMENT

All AEs must have their relationship to study treatment assessed by the Investigator who examines and evaluates the subject based on temporal relationship and his or her clinical judgment. Alternative

DocuSign Envelope ID: E4BE9C16-DB1E-4354-B874-2109B7254DAA

Efficacy and Safety of ANB019 in Subjects with Ichthyosis
Protocol ANB019-206

Version 1.0
30 October 2020

causes, such as underlying disease(s), concomitant therapy, and other risk factors, as well as the temporal relationship of the event to study treatment administration will be considered and investigated. The Investigator will also consult the IB in his or her assessment. The degree of certainty about causality will be graded using the categories below. In a clinical study, the study treatment must always be suspect.

- **Unrelated** – Clinical event incontrovertibly not related to the study treatment.
- **Unlikely to be related** – Clinical event with an incompatible time relationship to study treatment administration which makes a causal relationship improbable, and in which an underlying condition or other drugs or chemicals provides plausible explanations.
- **Possibly related** – Clinical event with a reasonable time relationship to study treatment administration, and that is unlikely to be attributed to concurrent condition or other drugs or chemicals.
- **Related** – Clinical event with plausible time relationship to study treatment administration and that cannot be explained by concurrent condition or other drugs or chemicals.

For each AE/SAE, the Investigator must document in the medical notes that he or she has reviewed the AE/SAE and has provided an assessment of causality.

There may be situations in which an SAE has occurred, and the Investigator has minimal information to include in the initial report to the pharmacovigilance unit. However, it is very important that the Investigator always make an assessment of causality for every event before the initial transmission of the SAE data to the pharmacovigilance unit within 24 hours of awareness of the event.

The Investigator may change his or her opinion of causality in light of follow-up information and send a SAE follow-up report with the updated causality assessment.

The causality assessment is one of the criteria used when determining regulatory reporting requirements.

8.2.1.3.3 EXPECTEDNESS

The pharmacovigilance unit will be responsible for determining whether an AE is expected or unexpected as interpreted through the IB. An AE will be considered unexpected if the nature, severity, or frequency of the event is not consistent with the risk information previously described for the study treatment.

8.2.1.4 TIME PERIOD AND FREQUENCY FOR EVENT ASSESSMENT AND FOLLOW-UP

The occurrence of an AE or SAE may come to the attention of study personnel during study visits and interviews of a study subject presenting for medical care, or upon review by a study monitor.

All AEs including local and systemic reactions will be captured on the appropriate eCRF. Information to be collected includes event description, date of onset, clinician's assessment of severity, seriousness, relationship to study treatment (assessed only by those with the training and authority to make a diagnosis), action taken, and outcome of the event. All AEs occurring while on study must be documented appropriately regardless of relationship (see [Section 8.2.1.3.2](#)). All AEs will be followed to adequate resolution.

Study site personnel will note the occurrence and nature of each subject's medical condition(s) present prior to the informed consent signature in the appropriate section of the source document and eCRF. During the study, site personnel will note any change in the condition(s) and the occurrence and nature of any AE. Care will be taken not to introduce bias when detecting AEs and/or SAEs. Open-ended and nonleading verbal questioning of the subject is the preferred method to inquire about AE occurrences.

DocuSign Envelope ID: E4BE9C16-DB1E-4354-B874-2109B7254DAA

Efficacy and Safety of ANB019 in Subjects with Ichthyosis
Protocol ANB019-206

Version 1.0
30 October 2020

Should a subject experience an AE at any time after the screening visit informed consent signature until the end of participation in the study, the event will be recorded as an AE in the source document and eCRF. Any SAE related to the study participation (eg, screening procedure) will be recorded in the source document and eCRF from the time consent is given to participate in the study until the end of participation in the study (EOS/ET visit).

Investigators are not obligated to actively seek AEs or SAEs after conclusion of the study participation. However, if the Investigator learns of any SAE, including a death, at any time after a subject has been discharged from the study, and he or she considers the event to be reasonably related to the study treatment or study participation, the Investigator must promptly notify the pharmacovigilance unit.

Any medical condition that is present at the time that the subject is screened will be considered as medical history and not reported as an AE. However, if the study subject's condition deteriorates at any time during the study, it will be recorded as an AE.

Changes in the severity of an AE/SAE will be documented to allow an assessment of the duration of the event at each level of severity to be performed. AEs characterized as intermittent require documentation of onset and duration of each episode.

The Investigator is responsible for appropriate medical care of subjects during the study. After the initial AE/SAE report, the Investigator is required to proactively follow each subject at subsequent visits/contacts. The Investigator also remains responsible for following through with an appropriate health care option for all AEs that are ongoing at the end of the study. The subject should be followed until the event is resolved or stable. If an AE is ongoing at the end of study, the follow-up duration is left to the discretion of the Investigator. Follow-up frequency will be performed at the discretion of the Investigator.

Whenever possible, clinically significant abnormal laboratory results are to be reported using the diagnostic that resulted in the clinically significant abnormal laboratory results and not the actual abnormal test.

8.2.1.5 ADVERSE EVENT REPORTING

When an AE/SAE occurs, it is the responsibility of the Investigator to review all documentation (eg, hospital progress notes, laboratory reports, and diagnostics reports) related to the event.

The Investigator will then record all relevant AE/SAE information (including event term, start and stop dates, severity, relationship to study treatment, outcome, if serious or non-serious) in the eCRF. Each event must be recorded separately.

It is not acceptable for the Investigator to send photocopies of the subject's medical records to the pharmacovigilance unit in lieu of completion of the AE/SAE eCRF page.

There may be instances when copies of medical records for certain cases are requested by the pharmacovigilance unit. In this case, all subject identifiers, with the exception of the subject number, will be redacted on the copies of the medical records before submission to the pharmacovigilance unit.

The Investigator will attempt to establish a diagnosis of the event based on signs, symptoms, and/or other clinical information. Whenever possible, the diagnosis (not the individual signs/symptoms) will be documented as the AE/SAE.

The Investigator is obligated to perform or arrange for the conduct of supplemental measurements and/or evaluations as medically indicated or as requested by the pharmacovigilance unit to elucidate the nature and/or causality of the AE or SAE as fully as possible. This may include additional laboratory

DocuSign Envelope ID: E4BE9C16-DB1E-4354-B874-2109B7254DAA

Efficacy and Safety of ANB019 in Subjects with Ichthyosis
Protocol ANB019-206

Version 1.0
30 October 2020

tests or investigations, histopathological examinations, or consultation with other health care professionals.

New or updated information will be recorded in the originally completed eCRF.

8.2.1.6 SERIOUS ADVERSE EVENT REPORTING

Prompt notification by the Investigator to the pharmacovigilance unit of an SAE is essential so that legal obligations and ethical responsibilities towards the safety of subjects and the safety of a study treatment under clinical investigation are met. All SAEs will be recorded and reported to the pharmacovigilance unit within 24 hours of awareness. The Investigator will submit any updated SAE data to the pharmacovigilance unit within 24 hours of receipt of the information as outlined in the Safety Reporting Instructions that will be provided to the sites and in the study Safety Management Plan.

The pharmacovigilance unit will inform the Medical Monitor, the Sponsor, and Innovaderm within 1 business day of awareness of a new SAE. The pharmacovigilance unit will process and evaluate all SAEs as soon as the reports are received. For each SAE received, the pharmacovigilance unit, in consultation with the Sponsor if needed, will make a determination as to whether the criteria for expedited reporting to relevant regulatory authorities have been met.

The Sponsor or designee has a legal responsibility to notify both the local regulatory authority and other regulatory agencies about the safety of a study treatment under clinical investigation. The Sponsor or designee will comply with country specific regulatory requirements relating to safety reporting to the regulatory authority, IRB/EC, and Investigators.

Investigator safety reports must be prepared for suspected unexpected SAEs according to local regulatory requirements and pharmacovigilance unit policy, and forwarded to Investigators as necessary.

An Investigator who receives an Investigator safety report describing an SAE or other specific safety information (eg, summary or listing of SAEs) from the pharmacovigilance unit will review and then file it along with the IB and will notify the IRB/EC, if appropriate according to local requirements.

If a subject dies while participating in the study, the Investigator will provide the pharmacovigilance unit with a copy of any postmortem findings.

8.2.1.6.1 REPORTING VIA AN ELECTRONIC DATA COLLECTION TOOL

The primary mechanism for reporting an SAE to the pharmacovigilance unit will be the EDC clinical database.

If the electronic system is unavailable, then the study center will use the back-up paper SAE Report Form. The study center will then enter the SAE data into the EDC system as soon as it becomes available.

After the study is completed and the database is locked, the tool system will be taken off-line to prevent the entry of new data or changes to existing data.

If a study center receives a report of a new SAE from a subject or receives updated data on a previously reported SAE after the EDC system is locked, then the study center can report this information on a paper SAE form and email the form to the pharmacovigilance unit.

Contacts for SAE reporting can be found in SAE form and Safety Reporting Instructions that will be provided to the sites.

DocuSign Envelope ID: E4BE9C16-DB1E-4354-B874-2109B7254DAA

Efficacy and Safety of ANB019 in Subjects with Ichthyosis
Protocol ANB019-206

Version 1.0
30 October 2020

8.2.1.6.2 REPORTING VIA PAPER CASE REPORT FORM

In rare circumstances, and in the absence of EDC or email, notification by facsimile or telephone is acceptable for notifying the pharmacovigilance unit of an SAE. Once the EDC is available, the SAE must be reported in the system within 24 hours of it becoming available.

Initial notification via telephone does not replace the need for the Investigator to complete and sign the SAE CRF pages within the designated reporting time frames.

Contacts for SAE reporting can be found in Safety Reporting Instructions that will be provided to the sites.

8.2.1.7 REPORTING EVENTS TO SUBJECTS

Not applicable.

8.2.1.8 REPORTING OF PREGNANCY

If a female subject or a female partner of a male subject becomes pregnant during the study and up to 28 days after the end of the study, the subject should inform the study center as soon as possible.

If a pregnancy is reported, the Investigator should inform the pharmacovigilance unit within 24 hours of learning of the pregnancy and should follow the procedures outlined in [Appendix 1](#).

If a pregnancy occurs, it will be followed up to determine the outcome, but no longer than 6 to 8 weeks after the estimated delivery date, where consent has been obtained to do so.

Abnormal pregnancy outcomes (eg, spontaneous abortion, fetal death, stillbirth, congenital anomalies, and ectopic pregnancy) are considered SAEs and must be reported in 24 hours of awareness as described in [Section 8.2.1.6](#).

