4.5 END OF STUDY DEFINITION

A subject is considered to have completed the study if he or she has completed all period of the study including the last specified visit (Day 281 [Week 40]/ET) shown in the SoA (see [Section 1.3](#)).

The end of the study is defined as completion of the last visit or procedure shown in the SoA by the last subject included the study.

DocuSign Envelope ID: E4BE9C16-DB1E-4354-B874-2109B7254DAA

Efficacy and Safety of ANB019 in Subjects with Ichthyosis
Protocol ANB019-206

Version 1.0
30 October 2020

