8. Contraceptive use by men and women should be consistent with local regulations regarding the methods of contraception for those participating in clinical studies.
Contraception and pregnancy:
 - a) A male subject must agree to use contraception as detailed in [Appendix 1](#) of this protocol during the treatment period and for at least 220 days (which includes the duration of relevant

DocuSign Envelope ID: E4BE9C16-DB1E-4354-B874-2109B7254DAA

Efficacy and Safety of ANB019 in Subjects with Ichthyosis
Protocol ANB019-206

Version 1.0
30 October 2020

exposure plus the duration of sperm cycle) after the last study treatment administration and refrain from donating sperm during this period.

b) Female subjects:

- A woman of childbearing potential (WOCBP) is eligible to participate if she has a negative serum pregnancy test (beta-human chorionic gonadotropin) at screening and a negative urine pregnancy test at Day 1 (see [Appendix 1](#)), is not breastfeeding, and agrees to follow the contraceptive guidance in Appendix 1 during the treatment period and for at least 6 months after receiving the study treatment, and refrains from donating oocytes for assisted reproduction during this period. The female subject's selected form of contraception must be effective by the time the female subject enters into the study at Day 1 (eg, hormonal contraception should be initiated at least 48 days before Day 1).
- A woman not of childbearing potential as defined in Appendix 1, must have a follicle-stimulating hormone (FSH) test confirming nonchildbearing potential.
- An adolescent subject who experiences menarche during the trial will be considered a WOCBP and will be required to follow the contraceptive guidance for WOCBP in Appendix 1 and undergo pregnancy testing as detailed in the SoA ([Section 1.3](#)).

9. Subject is willing to participate and is capable of giving written informed consent, which must be personally signed and dated by the subject and obtained prior to any trial-related activities. Subjects who need to provide assent, as per local requirement, need to have their parent(s) or legal representative read and sign the informed consent form prior to any study-related procedures. Adolescent subjects who reach 18 years of age during the study must be reconsented as adults.

10. Subject must be willing to comply with all study procedures and must be available for the duration of the study.

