6.7 TREATMENT AFTER THE END OF THE STUDY

All subjects will return to the study center for the EOS (Day 281/Week 40) or ET visit for final safety and EOS assessments. After this visit, subjects should be treated according to the clinical judgment of the subject's physician. Care after EOS/ET will not be provided by AnaptysBio, Inc. Any SAE or pregnancy occurring through the EOS visit should be reported to the pharmacovigilance unit (see [Section 8.2.1](#)) and followed up until an outcome is determined.

DocuSign Envelope ID: E4BE9C16-DB1E-4354-B874-2109B7254DAA

Efficacy and Safety of ANB019 in Subjects with Ichthyosis
Protocol ANB019-206

Version 1.0
30 October 2020

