In addition, male subjects must refrain from donating sperm for the duration of the study and for 220 days (which includes the duration of relevant exposure plus the duration of sperm cycle) after the last dose of study treatment.

Male subjects with a pregnant or breastfeeding partner must agree to remain abstinent from penile-vaginal intercourse or use a male condom during each episode of penile penetration for the

DocuSign Envelope ID: E4BE9C16-DB1E-4354-B874-2109B7254DAA

Efficacy and Safety of ANB019 in Subjects with Ichthyosis
Protocol ANB019-206

Version 1.0
30 October 2020

duration of the study and for 220 days (which includes the duration of relevant exposure plus the duration of sperm cycle) after the last dose of study treatment.

Female subjects

Female subjects of childbearing potential are eligible to participate if they agree to use highly effective methods of contraception consistently and correctly as described in the table below and during the protocol-defined time frame in [Section 5.1](#), and refrain from donating oocytes for assisted reproduction during this period.

DocuSign Envelope ID: E4BE9C16-DB1E-4354-B874-2109B7254DAA

Efficacy and Safety of ANB019 in Subjects with Ichthyosis
Protocol ANB019-206

Version 1.0
30 October 2020

Highly Effective Contraceptive Methods:

Highly Effective Contraceptive Methods That Are User Dependent^a

Failure rate of <1% per year when used consistently and correctly.

Combined (estrogen and progestogen containing) hormonal contraception associated with inhibition of ovulation

- Oral.
- Intravaginal.
- Transdermal.

Progestogen only hormonal contraception associated with inhibition of ovulation

- Oral.
- Injectable.

Highly Effective Methods That Are User Independent^a

Implantable progestogen only hormonal contraception associated with inhibition of ovulation

- Intrauterine device (IUD).
- Intrauterine hormone-releasing system (IUS).
- Implants inserted beneath the skin

Bilateral tubal occlusion.

Vasectomized Partner

A vasectomized partner is a highly effective birth control method provided that the partner is the sole male sexual partner of the WOCBP and the absence of sperm has been confirmed. If not, an additional highly effective method of contraception should be used.

Sexual Abstinence

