Sexual abstinence is considered a highly effective method only if defined as refraining from heterosexual intercourse during the entire period of risk associated with the study treatment. The reliability of sexual abstinence needs to be evaluated in relation to the duration of the study and the preferred and usual lifestyle of the subject.

NOTES:

^a Typical use failure rates may differ from those when used consistently and correctly. Use should be consistent with local regulations regarding the use of contraceptive methods for subjects participating in clinical studies.

Pregnancy Testing:

Women of childbearing potential should only be included after a confirmed menstrual period and a negative highly sensitive serum pregnancy test at screening and urine pregnancy test on Day 1 (prior to study treatment administration).

Additional pregnancy testing should be performed as mentioned in the SoA (see [Section 1.3](#)).

Pregnancy testing will be performed whenever a menstrual cycle is missed or when pregnancy is otherwise suspected. Positive urine pregnancy test result should be confirmed with serum test.

DocuSign Envelope ID: E4BE9C16-DB1E-4354-B874-2109B7254DAA

Efficacy and Safety of ANB019 in Subjects with Ichthyosis
Protocol ANB019-206

Version 1.0
30 October 2020

Collection of Pregnancy Information

Male subjects with partners who become pregnant

The Investigator will attempt to collect pregnancy information on any male subject's female partner who becomes pregnant while the male subject is in this study. This applies only to male subjects who receive study treatment.

After obtaining the necessary signed informed consent from the pregnant female partner directly, the Investigator will record pregnancy information on the appropriate pregnancy form and submit it to the pharmacovigilance unit within 24 hours of learning of the partner's pregnancy. The female partner will also be followed to determine the outcome of the pregnancy. Information on the status of the mother and child will be forwarded to the Sponsor. Generally, the follow-up will be no longer than 6 to 8 weeks following the estimated delivery date. Any termination of the pregnancy will be reported regardless of fetal status (presence or absence of anomalies) or indication for the procedure.

Any SAEs associated with the pregnancy in the male subject's partner should also be reported to the pharmacovigilance unit within 24 hours of the event using the back-up Paper Report Form.

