Female Subjects who become pregnant

The Investigator will collect pregnancy information on any female subject who becomes pregnant while participating in this study. Information will be recorded on the appropriate form and submitted to the pharmacovigilance unit within 24 hours of learning of a subject's pregnancy. The subject will be followed to determine the outcome of the pregnancy. The Investigator will collect follow-up information on the subject and the neonate and the information will be forwarded to the Sponsor. Generally, follow-up will not be required for longer than 6 to 8 weeks after the delivery date. Any termination of pregnancy will be reported, regardless of fetal status (presence or absence of anomalies) or indication for the procedure.

While pregnancy itself is not considered to be an AE or SAE, any pregnancy complication or elective termination of a pregnancy will be reported as an AE or SAE. A spontaneous abortion is always considered to be an SAE and will be reported as such.

Any poststudy pregnancy related SAE considered reasonably related to the study treatment by the Investigator will be reported to the Sponsor as described in [Section 8.2.1.8](#). While the Investigator is not obligated to actively seek this information in former subjects, he or she may learn of an SAE through spontaneous reporting.

Any female subject who becomes pregnant while participating in the study will be withdrawn from the study.

DocuSign Envelope ID: E4BE9C16-DB1E-4354-B874-2109B7254DAA

Efficacy and Safety of ANB019 in Subjects with Ichthyosis
Protocol ANB019-206

Version 1.0
30 October 2020

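### Pregnancy notification under Section 8.2.1.8 can close about 112 days after a completer's last dose, before the protocol's own contraception windows of 6 months (women) and 220 days (men) have run out

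*Protocol*

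**What the plan says.** Three places in the protocol set a period for pregnancy reporting, and each stops at a different point.

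- **Section 8.2.1.8** asks the subject to inform the site if a female subject or a male subject's partner "becomes pregnant during the study and up to 28 days after the end of the study". The site must pass on any pregnancy it hears of within 24 hours of learning of it, and that step has no end date.
- **Section 6.7** says: "Any SAE or pregnancy occurring through the EOS visit should be reported to the pharmacovigilance unit". It refers the reader to Section 8.2.1.
- **Appendix 1** says of women in the trial: "The Investigator will collect pregnancy information on any female subject who becomes pregnant while participating in this study". For men it covers "any male subject's female partner who becomes pregnant while the male subject is in this study".

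Section 4.5 gives the end of the study a trial-level meaning: "defined as completion of the last visit or procedure shown in the SoA by the last subject included the study". The same section separately says when an individual subject has completed.

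The contraception periods are in Section 5.1, criterion 8. Women must use contraception "during the treatment period and for at least 6 months after receiving the study treatment". Men must use it "during the treatment period and for at least 220 days" after the last administration, a period described as covering relevant exposure plus a sperm cycle.

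**The concern.** The contraception windows are the protocol's own statement of how long after dosing a conception calls for precaution. One would expect the request to report a pregnancy to last at least as long. Instead it is tied to the end of the study, while the contraception windows run from treatment. For a subject who completes dosing and follow-up, the reporting request can lapse first.

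The stake is completeness of pregnancy safety data. After notification closes, a pregnancy reaches the sponsor only if the subject volunteers it, or if the site learns of a serious outcome and judges it related. Section 8.2.1.4 does not oblige investigators to seek events once participation has ended, and the last scheduled pregnancy test is at the EOS visit. Pregnancies with normal outcomes are the most likely to be missed, and they form the denominator for the abnormal ones.

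**Working it through.** **Inputs**
- Last scheduled dose: Day 197 (Week 28), window ±4 days (Synopsis; Schedule of Activities).
- EOS visit: Day 281 (Week 40), window ±5 days (Schedule of Activities).
- Notification limit: 28 days after the end of the study (Section 8.2.1.8).
- Contraception: 220 days (men) and 6 months (women) (Section 5.1). Assumptions: 6 months is 183 days, counted from the last dose; a range of 181 to 184 days is also shown.

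**The plan's calendar reproduces.** 28 × 7 + 1 = 197 and 40 × 7 + 1 = 281.

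**Reading A: the subject's own EOS, completer**
- Last dose to EOS: 281 − 197 = 84 days.
- Notification closes: 84 + 28 = 112 days after the last dose.
- Gap, women: 183 − 112 = 71 days (181 − 112 = 69 to 184 − 112 = 72).
- Gap, partners of men: 220 − 112 = 108 days.

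With the visit windows, the shortest interval is (281 − 5) − (197 + 4) = 75 days and the longest is (281 + 5) − (197 − 4) = 93 days. Notification then closes at 75 + 28 = 103 to 93 + 28 = 121 days. The gap is 183 − 121 = 62 to 183 − 103 = 80 days for women, and 220 − 121 = 99 to 220 − 103 = 117 days for partners of men. It never reaches zero.

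**Reading B: Section 4.5, the last subject's last visit.** Let a completer's EOS fall *e* days before that date. Notification closes at 112 + *e* days after the last dose. The gap is 71 − *e* (women) or 108 − *e* (men), and is nil once *e* reaches 71 or 108. Accrual dates are not in the documents.

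**Section 6.7 taken alone (through EOS).** 183 − 84 = 99 days and 220 − 84 = 136 days.

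**Subjects who stop early, own-ET reading.** With the ET visit *d* days after the last dose:
- Gap, women: 183 − (*d* + 28) = 155 − *d*.
- Gap, men: 220 − (*d* + 28) = 192 − *d*.

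These exceed the completer's gap only if *d* is below 84, and are nil from *d* = 155 or 192. The documents do not give *d*. Section 7.1 asks subjects who stop dosing to complete the remaining procedures. One last dosed on Day 85 who stays to Day 281 is covered for 281 − 85 + 28 = 224 days and has no gap.

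**The case against.** **The defined term favours the protocol.** A reader might infer that every completer has a gap of 71 or 108 days. The documents do not support that: on the Section 4.5 definition the full gap is certain only for the last to finish. A rough planned-trial bound shows the scale. The synopsis gives about 25 months from first screening to completed analyses and 44 weeks per subject, so accrual spans at most about 25 × 30.4 − 308 = 452 days. If accrual were uniform (an assumption), 71/452 = 16% of women and 108/452 = 24% of men would have any gap. If analysis took 3 months (also assumed), the span would be 452 − 91 = 361 days and the shares 20% and 30%. This narrows the point but does not remove it. It also means that coverage depends on when a subject enrolled rather than on exposure.

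**Section 6.7 need not conflict.** A reader might infer a contradiction with Section 8.2.1.8. However, Section 6.7 does not say that later pregnancies are excluded, it cites Section 8.2.1, and it concerns reports to pharmacovigilance rather than the subject's notice to the site. It is loose wording.

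**Contraception length is one yardstick among several.** Nothing in the documents says that notification must match it, and the men's period adds a sperm cycle. With a half-life of about 28 days (Section 4.4), 112 days is 4 half-lives, leaving 0.5⁴ = 6%. The washout rule for prior antibodies (Section 5.2) is 12 weeks or 5 half-lives, here 5 × 28 = 140 days, which puts the shortfall at 140 − 112 = 28 days. The size therefore depends on the yardstick. Its direction does not, since even the latest own-EOS close, 121 days, falls before 140.

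**There is a safety net.** A reader might infer that harmful late outcomes go unreported. In fact pregnancies told to the site are forwarded, abnormal outcomes count as SAEs (Section 8.2.1.8), and poststudy SAEs that the site learns of and judges related remain reportable (Section 8.2.1.4; Appendix 1). This is a real mitigation, but a passive one.

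**The completer case did not arise.** SAP Section 3.1 says that no subject reached the open-label extension, so nobody received a Day 197 dose. This stands.

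**Conclusion.** The point holds as a cheap improvement to the protocol wording. On the own-EOS reading, the request to notify lapses inside the protocol's own precaution period for every completer on schedule, and nothing in the documents extends it. On the Section 4.5 reading it lapses early only for late finishers. The 112 days is the nominal figure; with visit windows the earliest close is 103 days.

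The figures rest on taking 6 months as 183 days, counting it from the last dose, and using the contraception windows as the measure of the period at risk. What is lost is mainly late pregnancies with normal outcomes and those that the site never hears of. No endpoint or analysis is affected, and the documents do not show that any actual pregnancy was missed. The consent form and the Safety Reporting Instructions are not among the documents and may already ask for more, so the point is limited to the protocol text.

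**What to change.** In Section 8.2.1.8, ask for notification of any pregnancy during the study and until the **later** of (a) 28 days after the end of the study and (b) 6 months (female subjects) or 220 days (partners of male subjects) after the subject's last dose. State whether the end of the study means the subject's own last visit or the Section 4.5 date. Align Section 6.7, the Appendix 1 collection paragraphs and the consent form.

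The later-of rule matters. Simply replacing the 28-day limit with a last-dose window would shorten coverage for some subjects. The woman last dosed on Day 85 who stays to Day 281 would drop from 224 to 183 days, a loss of 41. Early completers on the Section 4.5 reading could lose time too.

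The Section 7.2 withdrawal rule, visits, tests and contraception durations stay as they are. The cost is protocol and consent wording, plus an occasional late report. Each such report brings outcome follow-up to 6 to 8 weeks after the estimated delivery date, and separate consent where a partner is pregnant, all after the subject's last visit. Capture would still rely on subjects coming forward, so the gain is modest.
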